3.2.1. INCLUSION CRITERIA

Each subject must satisfy the following criteria at screening and baseline to be enrolled in the study:

1. Male or female adults ≥ 18 years and < 65 years of age at the time of signing the informed consent form (ICF). The minimum age for adults will depend on local regulations.
2. Have a diagnosis of SLE for at least 6 months prior to screening and fulfill the 1997 ACR (see Appendix 9.1) or 2012 Systemic Lupus International Collaborating Clinics (SLICC) classification criteria (see Appendix 9.2).
3. Have moderate to severe active SLE, for the purpose of this study defined by a SLEDAI-2K score ≥ 6 at screening.
4. Have at least one A or one B score on the revised BILAG-2004 criteria for the mucocutaneous and/or musculoskeletal system.
5. Have seropositive disease at screening for ANA ($\geq 1:80$) and/or anti-dsDNA (value above upper limit of laboratory normal range as measured by Farr assay) measured at the central laboratory.
6. Subject at least must be on one or more of the following treatments for SLE:
 - a. If subject is on oral corticosteroids, the dose should be equivalent to a maximum dose of 25 mg of prednisone/day and stable for at least 4 weeks prior to baseline.
 - b. If subject is on antimalarials, he or she must have received antimalarials for at least 12 weeks with a stable dose of max. 400 mg/day for at least 4 weeks prior to baseline.
 - c. If subject is on immunosuppressants: azathioprine (max. 150 mg/day), mycophenolate mofetil (max. 2.0 g/day), methotrexate (max. 25 mg/week), cyclosporine (max. 200 mg/day), leflunomide (max. 20 mg/day), treatment duration must be at least 12 weeks with a stable dose for at least 4 weeks prior to baseline; either alone or in combination with corticosteroids and/or hydroxychloroquine.
7. If immunosuppressants were previously given but have been stopped, the last dose should have been received more than 4 weeks prior to baseline; for leflunomide and hydroxychloroquine, a leflunomide or hydroxychloroquine treatment-free period of at least 12 weeks should be respected (unless an adequate cholestyramine wash-out was done for leflunomide).
8. If subject is on angiotensin-converting-enzyme (ACE) inhibitor or angiotensin receptor blocker, the dose should have been stable for 4 weeks prior to baseline.

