3.3.6.2. THERAPY STARTED AFTER FIRST DOSING

Standard of care therapy for SLE:

- The dose of oral corticosteroids (equivalent to ≤ 25 mg of prednisone/day) should be kept stable as much as possible through Week 24.
- As an exception, the protocol allows for both dose decrease (tapering) and dose increase with the following limits:
 - If necessary based on the Investigator's clinical judgment, initiation of a short period (maximum 1 week) increase of prednisone (up to a maximum dose of 15/20/25/30 mg/day depending on the baseline dose; see table below) is allowed until the Week 4 visit (i.e., Week 4 \pm 5 days) with a return to the baseline value by Week 12. This increase is not allowed if the disease activity improves.
 - In case lowering of the dose of prednisone is desired before the primary endpoint, tapering can be allowed up to Week 12 according to the specifications below:

	Baseline dose	Increase for max. 1 week during first 4 weeks	Tapering allowed between Baseline and Week 12
1	16 to 25 mg/day	Increase to a maximum of 30 mg/day	No dose decrease below 50% of baseline dose
2	11 to <16 mg/day	Increase to a maximum of 25 mg/day	No dose decrease below 75% of baseline dose
3	7.5 to <11 mg/day	Increase to a maximum of 20 mg/day	No dose decrease < 7.5 mg/day
4	<7.5 mg/day	Increase to a maximum of 15 mg/day	No tapering will be allowed

- Between Week 12 and Week 24, no increase nor decrease of the dose in prednisone is allowed.

- After Week 24, tapering of the dose of oral corticosteroids to a target of ≤ 7.5 mg/day by Week 40 is recommended, at a rate that can be decided by the Investigator as clinically indicated. While tapering the dose between Weeks 24 and 40, an increase to the dose preceding the last taper step will be allowed.
- Doses for concomitant antimalarials and/or immunosuppressants must be stable for the duration of the entire study. The dose may be reduced or the medication temporarily discontinued for abnormal laboratory values, side effects, concurrent illness, or the performance of a surgical procedure, but the dose change and reason should be clearly documented.

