- NSAIDs, including aspirin and selective cyclooxygenase 2 inhibitors and other analgesics for SLE-related symptoms during the study should receive the usual marketed doses approved in the country in which the study is being conducted. Doses must remain stable but may be changed at the discretion of the Investigator after Week 24 or if the subject develops unacceptable side effects.

Change to Standard of care therapy for SLE

In case of worsening of disease or a flare, the Investigator will decide on the need for increase of dose of oral corticosteroids, use of i.v. or i.m. corticosteroids, start or increase of the dose of anti-malarial or immunosuppressant. Subjects needing such change to standard of care therapy for SLE will be considered as treatment failures and imputed as non-responders in the analysis of the primary endpoint. This does not apply to the transient increase in oral corticosteroid (prednisone) dose that is allowed within the protocol until the Week 4 visit (i.e., Week 4 \pm 5 days) of the study (see above).

Prohibited Medication

Concomitant use of any of the following medications is prohibited while the subject is receiving the study drug and will prompt discontinuation of study drug:

- any investigational or biological drug.
- any live, attenuated vaccine within 3 months before dosing with ALX-0061, during the study or within 6 months after dosing.
- i.v. immunoglobulins, cyclophosphamide or tacrolimus.
- therapy blocking the IL-6 pathway, such as but not limited to ALX-0061, sirukumab, tocilizumab, sarilumab, clazakizumab, olokizumab, or JAK inhibitors.

Medicinal products which are metabolized via CYP450 3A4

Since IL-6 blocking might influence cytochrome P450 (CYP450) expression, subjects taking medicinal products which are metabolized via CYP450 3A4 (please refer to Flockhart, 2007

and Endres et al., 2006) will be closely monitored and their treatment will be adapted if necessary. For example, subjects on vitamin K antagonists will be monitored by assessment of international normalized ratio (INR) (see [Schedule of Assessments](#)), for subjects on statins, the lipid levels will be evaluated (see [Schedule of Assessments](#)), for subjects on cyclosporine, drug monitoring according to site routine practice should be performed.

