3.6.5. EVALUATION OF EFFICACY PARAMETERS

The adjudication committee will also evaluate appropriateness of data for evaluating the primary endpoint.

The primary endpoint is the percentage of subjects who achieved a response at Week 24 according to the composite mBICLA (BILAG-based Combined Lupus Assessment) score. BICLA responders are defined as subjects who meet all of the following criteria:

- (1) BILAG-2004 improvement: all A scores at baseline improved to B/C/D, and all B scores improved to C or D.
- (2) no worsening in disease activity: no new BILAG-2004 A scores and ≤ 1 new B score.
- (3) no worsening of total mSLEDAI-2K score from baseline.
- (4) no significant deterioration ($< 10\%$ worsening) in PGA.
- (5) no treatment failure (i.e., new or increased immunosuppressives or anti-malarials; or non-protocol allowed increased oral or parenteral corticosteroids; or premature discontinuation from study treatment).

The following efficacy analyses will be performed in addition to the primary analysis:

- Composite endpoint (m)BICLA over time (through Week 48) will be summarized by treatment group.
- Composite endpoint mSRI as well as standard SRI over time (through Week 48) will be summarized by treatment group.
- (m)SRI with more stringent (m)SLEDAI-cut-offs: SRI-5, SRI-6, SRI-7, SRI-8 over time (through Week 48) will be summarized by treatment group.
- Change from baseline in mSLEDAI-2K total score as well as standard SLEDAI-2K measured over time (through Week 48) will be summarized by treatment group.
- Number and percent of subjects with BILAG-2004 improvement.
- BILAG-2004 (total score) over time (through Week 48) will be summarized by treatment group.
- Improvement in individual organ systems of the BILAG-2004 over time (through Week 48) will be summarized by treatment group.

- Number of BILAG-2004 systems in which activity increased, decreased or remained the same compared to previous visit (BILAG-2004 systems tally) over time (through Week 48) will be summarized by treatment group.
- Change from baseline in PGA over time (through Week 48) will be summarized by treatment group.
- Change from baseline in patient's global assessment over time (through Week 48) will be summarized by treatment group.
- Change from baseline in proteinuria/urine sediment/serum creatinine/eGFR over time (through Week 48) will be summarized by treatment group.

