- Proportion of treatment failures (defined as non-protocol allowed increase in steroid dose, start i.v. or i.m. steroids, start or increase of immunosuppressant) at Week 24 and at Week 48 will be summarized by treatment group.
- Reduction in flare rate at Week 24 and at Week 48.
 - Severe flare defined as a new A score in any system of the BILAG-2004 index; moderate flare defined as a new B score following a C, D or E score.
 - SFI.
- Percent change from baseline in daily dose of steroids at Week 24 and 48 will be summarized by treatment group.
- Percent subjects whose prednisone equivalent dose was >7.5 mg/day at baseline and reduced to ≤ 7.5 mg/day during Weeks 40–48 without experiencing a flare will be summarized by treatment group.
- Percent subjects who are able to discontinue prednisone by Week 48 without experiencing a flare will be summarized by treatment group.
- Changes from baseline in the physical and mental component scores of SF-36 at Week 24 and at Week 48 will be summarized by treatment group.
- 28 Joints count over time and change from baseline in 28 joint count over time will be summarized by treatment group.
- CLASI over time and change from baseline evaluation at Week 12, 24 and Week 48 will be summarized by treatment group.
- PK parameters.
- PD markers, including total sIL-6R, CRP, fibrinogen, anti-dsDNA, C3, C4, CH50.

Descriptive subgroup analyses may be performed to evaluate consistency of the primary endpoint over covariates including demographics (including weight and region), baseline disease, and prior and concomitant medications. Details will be provided in the SAP.

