3.6.5.1. PRIMARY EFFICACY ENDPOINT

mBICLA response rates at Week 24 will be analyzed using the MCP-Mod methodology [1]. The method entails a unified strategy to the analysis of data from dose-response studies which combines multiple comparison and modeling techniques. In general, the existence of several candidate parametric models is assumed and multiple comparison techniques are used to choose the model most likely to represent the true underlying dose-response curve,

while preserving the family-wise error rate. The selected model may further be used to guide the choice of adequate doses.

The analysis will be performed using the mITT population of all subjects who have received at least 1 administration of study drug and according to the treatment for which they were assigned.

Subjects with missing mBICLA response at Week 24, including those who have discontinued study drug before Week 24, as well as subjects with treatment failure, will be treated as non-responders (non-response imputation approach). Treatment failure is defined as non-protocol allowed increase in steroid dose, start i.v. or i.m. steroids, start or increase of immunosuppressant. Details on how missing mBICLA response is defined and handled will be provided in the SAP.

Primary efficacy endpoint evaluation will also be performed using the PP population.

Summary statistics (frequencies, proportions) for mBICLA response rate at Week 24 will be provided by treatment group.

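### Treatment failure, as defined for the secondary endpoint and in the primary analysis text, omits started or increased anti-malarials, which mBICLA criterion (5) and the therapy-change rules count as failure

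*Protocol*

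**What the plan says.** The protocol defines treatment failure in two ways.

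The wider definition is criterion (5) of the mBICLA response in Section 3.6.5: "new or increased immunosuppressives or anti-malarials; or non-protocol allowed increased oral or parenteral corticosteroids; or premature discontinuation from study treatment". The synopsis (primary endpoint) and Section 3.4.3.6 define it the same way.

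The rules for changing standard-of-care therapy agree with it on anti-malarials. Section 3.3.6.2 lets the Investigator respond to worsening or flare with, among other things, "start or increase of the dose of anti-malarial or immunosuppressant", and continues: "Subjects needing such change to standard of care therapy for SLE will be considered as treatment failures and imputed as non-responders in the analysis". The rule is limited there to the primary endpoint. Section 3.2.3.2 and item f) of the synopsis text on standard-of-care medication carry the same rule.

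The narrower definition is in the primary analysis text of Section 3.6.5.1: "Treatment failure is defined as non-protocol allowed increase in steroid dose, start i.v. or i.m. steroids, start or increase of immunosuppressant". The secondary endpoint in Section 3.6.5 uses the same list: "Proportion of treatment failures (defined as non-protocol allowed increase in steroid dose, start i.v. or i.m. steroids, start or increase of immunosuppressant", reported at Weeks 24 and 48. The synopsis repeats both, under secondary endpoints and under statistical methods.

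**The concern.** A subject who worsens and is given only a new or increased anti-malarial is a treatment failure under criterion (5) and under Section 3.3.6.2. Under the definitions in Sections 3.6.5 (secondary endpoint) and 3.6.5.1 the same subject is not.

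Two things follow. First, Section 3.6.5.1 contradicts Section 3.3.6.2 and criterion (5) on who counts as a treatment failure in the same primary analysis. Second, the secondary proportion, taken literally, leaves out one kind of rescue that the rest of the protocol treats as failure. That proportion stands beside a composite whose reporting covers the same weeks: "Composite endpoint (m)BICLA over time (through Week 48) will be summarized by treatment group".

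**Working it through.** The plan states no figure to reproduce here. The check is a comparison of texts, followed by one conversion to percentage points.

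**Step 1: what each definition counts.**

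| Place in the protocol | Steroid changes not allowed by protocol | Immunosuppressant started or increased | Anti-malarial started or increased | Premature discontinuation |
|---|---|---|---|---|
| Criterion (5): synopsis, 3.4.3.6, 3.6.5 | yes | yes | **yes** | yes |
| Therapy-change rules: synopsis item f), 3.2.3.2, 3.3.6.2 | yes | yes | **yes** | not part of the rule |
| Primary analysis text: synopsis, 3.6.5.1 | yes | yes | **no** | handled separately |
| Secondary endpoint: synopsis, 3.6.5 | yes | yes | **no** | not listed |

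**Step 2: does the word immunosuppressant already cover anti-malarials?** Inclusion criterion 6 in Section 3.2.1 gives anti-malarials their own item, 6b. Item 6c then names the other class: "immunosuppressants: azathioprine (max. 150 mg/day), mycophenolate mofetil (max. 2.0 g/day), methotrexate (max. 25 mg/week), cyclosporine (max. 200 mg/day), leflunomide (max. 20 mg/day"). Hydroxychloroquine appears in 6c only as a possible combination partner. Section 3.3.6.2 names the two classes side by side: "Doses for concomitant antimalarials and/or immunosuppressants must be stable for the duration of the entire study". Criterion (5) and the therapy-change rules also name both, which would be redundant if one term contained the other. The omission is therefore one of substance.

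**Step 3: can the case arise?** Yes. Inclusion criterion 6 asks for at least one of the listed treatment classes, so a subject may enter without an anti-malarial. Section 3.3.6.2 lets the Investigator start one, or raise an existing dose, for worsening.

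**Step 4: effect on the primary endpoint.** A subject must meet all five criteria to be an mBICLA responder, so an anti-malarial rescue fails criterion (5) whatever Section 3.6.5.1 lists. Effect on the primary response rate if criterion (5) is applied: 0.

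**Step 5: effect on the secondary proportion.** Let k be the number of subjects in an arm rescued with an anti-malarial and nothing else on the list. With the planned 60 per arm, the shortfall is k/60:

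- k = 0: 0 points
- k = 1: 1/60 = 0.0167, or 1.7 points
- k = 3: 3/60 = 0.050, or 5.0 points

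These values of k only show the scale and are not forecasts; the protocol gives no rate.

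Section 3.6.5.2 summarises secondary endpoints on observed data in the mITT population. If the 15% discontinuation assumed in Section 3.6.3 removed subjects from the denominator, 60 × 0.85 = 51 would remain and one case would be 1/51, about 2.0 points. The order of magnitude is the same.

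**The case against.** **Terminology.** Inclusion criterion 7 and the matching text in Section 3.3.6.1 mention hydroxychloroquine inside the rule on stopped immunosuppressants, which gives some support to a broad reading of that word. The support is weak: it comes from one washout rule, against the consistent separation shown in Step 2.

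**Scope of the therapy-change rules.** These rules speak of the primary endpoint analysis and do not expressly define the secondary proportion, which has its own computable definition. This stands, so the secondary endpoint does not strictly break a conduct rule. It does not reconcile Section 3.6.5.1 with Section 3.3.6.2, since both concern the primary analysis. Nor does any text say that the narrower list was intended for the secondary endpoint.

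**Deferral to the SAP.** Section 3.6.5.1 leaves to the SAP how missing mBICLA response is defined and handled, and Section 3.6.2 leaves analysis details in general. Treatment failure is not left open: the protocol defines it, in two ways that conflict.

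**Frequency.** Section 1.1.1 says that on worsening hydroxychloroquine is usually kept, other therapy is added and steroid doses are usually raised. A subject with a steroid increase outside the protocol limits is already counted, so only anti-malarial-only rescue is missed. This stands, and it argues against any large estimate.

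**Discontinuation.** A reader might infer that the secondary endpoint is also wrong to leave out premature discontinuation. The documents do not support that. The therapy-change rules tie failure to changes in treatment, and Section 3.6.5.1 names discontinuers separately, so a measure limited to therapy changes is a legitimate choice.

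**Conclusion.** The definition is wrong as written in four places: the secondary endpoint and the primary analysis text, each in the synopsis and in the body. The severity is minor.

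A reader might infer that the primary analysis is biased because Section 3.6.5.1 carries the narrower list. It is not, provided criterion (5) is applied as stated; what remains there is a contradiction in the text. The only result affected is one descriptive proportion at Weeks 24 and 48, with no test attached. It loses about 1.7 points in an arm of 60 for each subject rescued with an anti-malarial alone. How many such subjects there will be cannot be derived from the protocol. The number may be zero, and the background section suggests that such cases are not typical.

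The conclusion rests on reading immunosuppressant as inclusion criterion 6 and Section 3.3.6.2 use it, as a class that does not include anti-malarials.

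**What to change.** In Sections 3.6.5 (secondary endpoint) and 3.6.5.1, and in the two matching synopsis entries, insert *anti-malarial or* before *immunosuppressant* in the last item of the treatment-failure list. All definitions then agree on which therapy changes count.

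The cost is a short wording change in four places. No new data are needed, because Section 3.3.6 already has concomitant medication recorded up to the Follow-up Visit. The downside is that reported failure proportions may rise slightly. The endpoint needs no new name, no extra table rows and no change of denominator.

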3.6.5.1. PRIMARY EFFICACY ENDPOINT

mBICLA response rates at Week 24 will be analyzed using the MCP-Mod methodology [1]. The method entails a unified strategy to the analysis of data from dose-response studies which combines multiple comparison and modeling techniques. In general, the existence of several candidate parametric models is assumed and multiple comparison techniques are used to choose the model most likely to represent the true underlying dose-response curve,

while preserving the family-wise error rate. The selected model may further be used to guide the choice of adequate doses.

The analysis will be performed using the mITT population of all subjects who have received at least 1 administration of study drug and according to the treatment for which they were assigned.

Subjects with missing mBICLA response at Week 24, including those who have discontinued study drug before Week 24, as well as subjects with treatment failure, will be treated as non-responders (non-response imputation approach). Treatment failure is defined as non-protocol allowed increase in steroid dose, start i.v. or i.m. steroids, start or increase of immunosuppressant. Details on how missing mBICLA response is defined and handled will be provided in the SAP.

Primary efficacy endpoint evaluation will also be performed using the PP population.

Summary statistics (frequencies, proportions) for mBICLA response rate at Week 24 will be provided by treatment group.

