f) In case of worsening of disease or a flare, the Investigator will decide on the need for increase of dose of oral corticosteroids, use of i.v. or i.m. corticosteroids, start or increase of the dose of anti-malarial or immunosuppressant, according to his/her local clinical practice. The Investigator can also decide on whether study drug can be continued or not. Subjects needing such change to standard of care therapy for SLE will be considered as treatment failures and imputed as non-responders in the analysis of the primary endpoint. This does not apply to the transient increase in oral corticosteroid dose that is allowed within the protocol until the Week 4 visit (Week 4 \pm 5 days; see above).

Study Duration:

The anticipated maximum study duration per subject is 58 weeks after randomization; subjects will be followed for efficacy through Week 48 and for safety through Week 58.

The end of study is defined as the time of the last visit of the last subject participating in the study.

- **Screening Period:**
Subjects will be screened to confirm their eligibility for participation in this study within 4 weeks prior to baseline.
- **Treatment and Assessment Period:**
Eligible subjects will receive treatment at Week 0/Day 1 and up to and including Week 46. Subjects will return for ambulatory visits every 2 weeks.
All post-baseline visits may occur at the indicated week \pm 5 days throughout the study.

- Final Visit/ Early Termination Visit:
 - Subjects should return for the assessment visit at Week 48, and for the Follow-Up Visit at Week 58 (12 weeks after the last study drug administration at Week 46).
 - Subjects who discontinue study drug but are not withdrawing consent for post-treatment follow-up, should return for an early termination visit within 3 weeks after the last study drug administration. Subjects should also return for a Follow-up Visit 12 weeks after last study drug administration.

For details on visit assessments, see the Schedule of Assessments.

Discontinuation criteria:

Study drug administration must be discontinued in case of:

- Withdrawal of consent.
- Serious hypersensitivity reaction.
- Abnormalities in laboratory test results:
 - ALT and/or AST elevations:
 - $> 3 - \leq 5 \times \text{ULN}$, confirmed by repeat testing on 2 consecutive visits
 - $> 5 \times \text{ULN}$ (CTCAE \geq grade 3)
 - absolute neutrophil count $< 1 \times 10^9/\text{L}$ (CTCAE \geq grade 3)

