Secondary endpoints will include:

- Composite endpoint (m)BICLA over time.
- Composite endpoint mSRI as well as standard SRI over time.
- (m)SRI with more stringent (m)SLEDAI-cut-offs: SRI-5, SRI-6, SRI-7, SRI-8 over time.
- Change from baseline in mSLEDAI-2K total score as well as standard SLEDAI-2K measured over time.
- Number and percent of subjects with BILAG-2004 improvement.
- BILAG-2004 (total score) over time.
- Improvement in individual organ systems of the BILAG-2004 over time.
- Number of BILAG-2004 systems in which activity increased, decreased or remained the same compared to previous visit (BILAG-2004 systems tally) over time.
- Change from baseline in PGA over time.
- Change from baseline in patient's global assessment over time.
- Change from baseline in proteinuria/urine sediment/serum creatinine/eGFR over time.
- Proportion of treatment failures (defined as non-protocol allowed increase in steroid dose, start i.v. or i.m. steroids, start or increase of immunosuppressant) at Week 24 and at Week 48.

- Reduction in flare rate at Week 24 and at Week 48.
 - Severe flare defined as a new A score in any system of the BILAG-2004 index; moderate flare defined as a new B score following a C, D or E score.
 - SLEDAI flare index (SFI).
- Percent change from baseline in daily dose of steroids at Week 24 and 48.
- Percent subjects whose prednisone equivalent dose was >7.5 mg/day at baseline and reduced to ≤7.5 mg/day during Weeks 40–48 without experiencing a flare.
- Percent subjects who are able to discontinue prednisone by Week 48 without experiencing a flare.
- Changes from baseline in the physical and mental component scores of SF-36 at Week 24 and at Week 48.
- 28 Joints count over time and change from baseline in 28 joint count over time.
- Cutaneous lupus erythematosus disease area and severity index (CLASI) over time and change from baseline evaluation at Week 12, 24 and Week 48.
- PK parameters.
- PD markers, including total sIL-6R, CRP, fibrinogen, anti-dsDNA, C3, C4, CH50.

Pharmacokinetics

Samples for determination of ALX-0061 serum levels.

Pharmacodynamics

Samples for determination of biomarker levels, including but not limited to total sIL-6R, CRP, fibrinogen, anti-dsDNA, C3, C4, CH50.

Samples for determination of additional biomarker levels (exploratory), including but not limited to uMCP-1, plasma cells, T helper 17 (Th17) and regulatory T (Treg) cells.

Immunogenicity

Samples for determination of anti-ALX-0061 antibodies.

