In case of worsening of disease or a flare, the Investigator will decide on the need for increase of dose of oral corticosteroids, use of i.v. or i.m. corticosteroids, start or increase of the dose of anti-malarial or immunosuppressant, according to his/her local clinical practice. The Investigator will also assess if study drug administration can be continued or not, except in case of initiation of forbidden treatment e.g., cyclophosphamide or another biologic, when study drug administration will be discontinued. Subjects needing such change to standard of care therapy for SLE will be considered as treatment failures and imputed as non-responders in the analysis of the primary endpoint. This does not apply to the transient increase in oral corticosteroid dose that is allowed within the protocol until the Week 4 visit (i.e., Week 4 \pm 5 days).

A description of assessments to be performed for subjects who discontinue from the study or study drug is provided in section 3.4.1.3 (also see Early Termination Visit in the [Schedule of Assessments](#)).

For all subjects, every effort should be made to contact the Medical Monitor prior to discontinuing study drug administration, where medically feasible. If there is a medical reason for discontinuation, the subject will remain under the supervision of the Investigator until satisfactory health has returned unless the subject withdraws his/her consent and is no longer willing to come to the visits. Subjects who discontinue will not be replaced.

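### The treatment-failure definition in 3.6.5.1, the synopsis and the secondary failure endpoint omits antimalarials, which mBICLA criterion (5) and the rule on changes to standard of care both count

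*Protocol*

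**What the plan says.** The protocol describes treatment failure in two ways.

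**Without antimalarials.** Section 3.6.5.1 states: "Treatment failure is defined as non-protocol allowed increase in steroid dose, start i.v. or i.m. steroids, start or increase of immunosuppressant". The synopsis repeats this under the primary efficacy evaluation. The secondary endpoint in 3.6.5 uses the same list: "Proportion of treatment failures (defined as non-protocol allowed increase in steroid dose, start i.v. or i.m. steroids, start or increase of immunosuppressant". The synopsis list of secondary endpoints agrees with it.

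**With antimalarials.** Criterion (5) of the responder definition in 3.6.5 reads "no treatment failure (i.e., new or increased immunosuppressives or anti-malarials" and goes on to non-permitted steroid increases and premature discontinuation of study treatment. The synopsis and section 3.4.3.6 carry the same criterion. Section 3.3.6.2 describes the changes an investigator may make on worsening or flare and ends: "anti-malarial or immunosuppressant. Subjects needing such change to standard of care therapy for SLE will be considered as treatment failures". Section 3.2.3.2 and item (f) of the synopsis section on standard of care medication say the same, each naming "start or increase of the dose of anti-malarial or immunosuppressant".

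**The concern.** The shorter definition is a closed list: it says what failure is and gives no sign that it is only a set of examples. A subject whose only change is a new or increased antimalarial is a failure under criterion (5) and under the standard-of-care rule, but not under 3.6.5.1 or the secondary endpoint.

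Two things are at stake. First, the secondary failure proportion, followed as written, leaves out subjects whom the protocol elsewhere calls failures. The failure table and the mBICLA non-responder counts would then not reconcile. Second, 3.6.5.1 is the section that states the non-responder imputation rule. If its list were programmed in place of criterion (5), a subject rescued with an antimalarial could be counted as a primary responder.

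**Working it through.** **1. Definitions side by side**

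| Place in protocol | Antimalarial start or increase | Premature discontinuation |
|---|---|---|
| 3.6.5.1; synopsis, primary evaluation | not listed | not in the failure list, but imputed as non-response before Week 24 |
| 3.6.5 and synopsis, secondary proportion of failures | not listed | not listed |
| Criterion (5): 3.6.5, 3.4.3.6, synopsis | failure | failure |
| 3.3.6.2, 3.2.3.2, synopsis item (f) | failure and non-responder | not addressed in this rule |

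Section 3.6.5 disagrees with itself and with its own subsection 3.6.5.1. The synopsis also disagrees with itself.

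**2. Can the word immunosuppressant be read to include antimalarials?** The protocol's own usage is against it. Inclusion criterion 6 in 3.2.1 puts antimalarials under (b) and immunosuppressants under (c), and (c) names its drugs without an antimalarial. The stable-dose rule in 3.3.6.2 names both: "Doses for concomitant antimalarials and/or immunosuppressants must be stable for the duration of the entire study". Criterion (5) and the standard-of-care rule also name both, which would be redundant if one term covered the other. The exception is inclusion criterion 7, repeated in 3.3.6.1, where hydroxychloroquine appears in a sentence about stopped immunosuppressants.

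**3. Can an antimalarial-only change occur?** Yes. Inclusion criterion 6 asks for at least one of the listed treatments, so a subject on corticosteroids alone is eligible and can start an antimalarial later. The standard-of-care rule provides for this.

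**4. Size, secondary proportion.** Input: 60 subjects per arm (3.6.3). The understatement in an arm is k/60, where k is the number of antimalarial-only failures.

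- k = 1: 1/60 = 1.7 points
- k = 3: 3/60 = 5.0 points

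The protocol gives no value for k. The range 1 to 3 is an assumption, and k could be 0.

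**5. Discontinuation, secondary proportion only.** Section 3.6.3 assumes 15% discontinuation, equal across arms: 0.15 × 60 = 9 subjects per arm. Relative to criterion (5), the secondary proportion leaves out up to 9 of 60. This is an upper bound, because some of them may already count through a treatment change.

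**6. Size, primary endpoint.** With criterion (5) applied: 0 points. If the list in 3.6.5.1 replaced it: at most 1/60 = 1.7 points per missed subject, and only where that subject also meets criteria (1) to (4). Discontinuation before Week 24 adds nothing here, because 3.6.5.1 already makes those subjects non-responders.

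**The case against.** The strongest reply is that the primary endpoint is protected twice. A responder must meet all five criteria, and the fifth names antimalarials. Separately, 3.3.6.2 imputes such subjects as non-responders. On this reading the sentence in 3.6.5.1 only adds non-responders and cannot turn a criterion (5) failure into a responder. This largely stands: the primary result is at risk only if a programmer takes the 3.6.5.1 list as the operative rule.

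The remaining endpoint is also descriptive. Section 3.6.5.2 plans summaries by treatment group, and no test or sample size rests on the failure proportion. The number of antimalarial-only failures is unknown, since anyone also given a non-permitted steroid increase or an immunosuppressant is already counted. Secondary endpoints use observed data, so 60 may not be the actual denominator. A treatment-change endpoint that excludes discontinuation may be intended. All of this limits the size of the problem.

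It does not remove the contradiction. Criterion 7 shows loose drafting, which is a reason to state the definition once. Nor is this left to the statistical analysis plan: 3.6.5.1 defers how missing mBICLA response is defined and handled, but states the failure definition outright. An analysis plan can follow one protocol definition only by departing from the other.

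**Conclusion.** The concern holds. Treatment failure has two conflicting definitions, and the difference between them that matters is antimalarials. The certain consequence is in the secondary proportion of treatment failures at Weeks 24 and 48, which omits antimalarial-only failures. Its size depends on an assumed count of such subjects and on the planned 60 per arm as denominator. The effect on the primary endpoint is nil provided criterion (5) is what is programmed. The consequence is modest, but the contradiction is plain from the text and should be corrected before database lock.

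**What to change.** State one treatment-failure definition for analysis that includes new or increased antimalarials, in line with criterion (5). Refer to it from 3.6.5.1, from the secondary endpoint in 3.6.5 and from both places in the synopsis, instead of restating a shorter list. For the secondary proportion, report treatment-change failures and premature discontinuations as separate components, so that the table reconciles with the mBICLA non-responder count whichever total a reader wants.

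One clarification can be made in the same edit. Criterion (5) speaks of parenteral corticosteroids, while the shorter list names only the intravenous and intramuscular routes. The text should say whether a post-baseline intra-articular steroid counts for the endpoint.

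The cost is wording only. Section 3.3.6 already has concomitant medication recorded up to the Follow-up Visit, so no new data are needed, and the rules on patient management do not change. Reported treatment-change failure proportions would stay the same or rise slightly, according to how many antimalarial-only failures occur.
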